## VT 18-535 Short Term Choline Supplementation and Cardiovascular Health in Adults

**Physical Activity:** Subjects will be asked to complete a questionnaire regarding usual daily activities. They will also be asked to wear a device called an accelerometer over a 4-day period to measure their physical activity level

**Infection/Inflammation Questionnaire:** Subjects will be asked to complete a questionnaire about any recent illnesses or infections that they may have had in the prior month.

**Dietary Record:** Subjects will be asked to record/recall all of the food they eat during a 4-day period.

**Body mass and height:** Body weight will be measured on a digital scale accurate to +0.01 kg. Height will be measured with a stadiometer

**Resting Blood Pressure and Heart Rate:** Blood pressure measurements will be made under quiet, comfortable ambient laboratory conditions via mercury sphygmomanometry or an automatic blood pressure monitor. Heart rate will also be determined by an automatic blood pressure cuff. Measurements will conform strictly to American Heart Association guidelines.

Session 2, 8, 11, 17: (Approximately 3 hours) Garvin Building, Suite 1575

**Overnight Fast:** Subjects will be asked to avoid eating or drinking anything except water and to avoid consuming any caffeine-containing beverages for 12 hours prior to this visit so that the test results will not be influenced by the food they eat or by the normal digestion process.

**Resting Blood Pressure and Heart Rate:** Blood pressure measurements will be made under quiet, comfortable ambient laboratory conditions via mercury sphygmomanometry or an automatic blood pressure monitor. Heart rate will also be determined by an automatic blood pressure cuff. Measurements will conform strictly to American Heart Association guidelines.

**Body Mass:** Body weight will be measured on a digital scale accurate to +/- 0.01 kg.

**Dietary intake analysis (24-hour recall):** Subjects will be asked to recall all the food and beverages they consumed in the previous 24-hour period.

**Oral Glucose Tolerance Test:** One small plastic tube (catheter) will be placed in one of the subject's arm veins. After a baseline blood draw to measure glucose, insulin, cholesterol, and other factors that may impact or be reflective of the subject's health status (e.g., C-reactive protein), the subject will drink a sugary drink of glucose (75 grams) and blood will be collected in small amounts (less than one half teaspoon) every half hour (4 blood draws total) for a 2-hour period.

## VT 18-535 Short Term Choline Supplementation and Cardiovascular Health in Adults

**Stool Collection:** Subjects will be given a test tube and asked to collect a stool sample. Subjects will be asked to bring the sample back to the laboratory during their next scheduled visit. All supplies and instructions will be provided by the laboratory.

**Continuous Glucose Monitoring:** Glucose will be measured by a continuous glucose monitor (FreeStyle Libre Pro, Abbott). A small sensor will be placed on the subject's skin overlying the back side of their arm in order to measure glucose continuously. The sensor has a small plastic tube that is inserted into the tissue just below the skin and is held in place with sticky tape. The device will be worn for 3-4 days.

Session 3, 9, 12, 18: (Approximately 2 hours) Garvin Building, Suite 1575

**Overnight Fast:** Subjects will be asked to avoid eating or drinking anything except water and to avoid consuming any caffeine-containing beverages for 12 hours prior to this visit so that the test results will not be influenced by the food they eat or by the normal digestion process.

**Resting Blood Pressure and Heart Rate:** Blood pressure measurements will be made under quiet, comfortable ambient laboratory conditions via mercury sphygmomanometry or an automatic blood pressure monitor. Heart rate will also be determined by an automatic blood pressure cuff. Measurements will conform strictly to American Heart Association guidelines.

**Body Mass:** Body weight will be measured on a digital scale accurate to +/- 0.01 kg.

**Dietary intake analysis (24-hour recall):** Subjects will be asked to recall all the food and beverages they consumed in the previous 24-hour period.

**Blood Chemistry:** A blood draw will be collected for choline concentrations as well as glucose, cholesterol, and other factors that may impact or be reflective of vascular function/health. A needle will be inserted in an arm vein to draw blood (approximately 2 tablespoons/draw).

**Arterial Stiffness:** Carotid Ultrasonography - Common carotid artery diameters will be measured from the image obtained from an ultrasound unit (GE Vivid S6) equipped with a high-resolution linear array transducer. Applanation Tonometry - The carotid, brachial, radial and femoral artery pressure waveform and amplitude will be obtained by a fingertip probe incorporating a high-fidelity strain gauge transducer.

**Brachial Artery Flow Mediated Dilatation (FMD):** FMD of the brachial artery will be assessed using duplex ultrasonography (GE Vivid S6) with a high-resolution linear array transducer according to published guidelines. Reactive hyperemia will be produced by inflation of a pediatric BP cuff around the forearm for 5 minutes. Offline analysis of baseline and post-reactive hyperemic diameters and velocities will be performed using edge detection software (Vascular Analysis Tools, Medical Imaging Applications, Inc.).

## VT 18-535 Short Term Choline Supplementation and Cardiovascular Health in Adults

Endothelium Independent Vasodilation: This will be assessed by measuring brachial arterial dilation for 5 minutes following administration of 0.4 mg of sublingual nitroglycerine. Individuals will not be allowed to participate in this aspect if they take Cialis or Viagra or have a history of coronary heart disease.

24-hour Urine Collection: Subjects will be asked to collect all urine samples over a 24-hour period and bring the sample back to the laboratory during their next scheduled visit. All supplies and instructions will be provided by the laboratory.

Body Mass and Composition: Body weight will be measured on a digital scale accurate to +0.01 kg. Height will be measured with a stadiometer. Percent body fat and fat-free mass will be measured in all subjects using dual-energy x-ray absorptiometry (DEXA) (Prodigy Advance, GE Healthcare).

Pregnancy Test: If a subject is female and pre- or peri-menopausal or not postmenopausal for at least 1 year, she will be required to provide a small cup of urine for a pregnancy test.

Session 4, 10, 13, 19: (Approximately 3 hours) Garvin Building, Suite 1575

Overnight Fast: Subjects will be asked to avoid eating or drinking anything except water and to avoid consuming any caffeine-containing beverages for 12 hours prior to this visit so that the test results will not be influenced by the food they eat or by the normal digestion process.

Resting Blood Pressure and Heart Rate: Blood pressure measurements will be made under quiet, comfortable ambient laboratory conditions via mercury sphygmomanometry or an automatic blood pressure monitor. Heart rate will also be determined by an automatic blood pressure cuff. Measurements will conform strictly to American Heart Association guidelines.

Body Mass: Body weight will be measured on a digital scale accurate to +/- 0.01 kg.

Dietary intake analysis (24-hour recall): Subjects will be asked to recall all the food and beverages they consumed in the previous 24-hour period.

Mixed Meal Tolerance Test: A small plastic tube (catheter) will be placed in one of the subject's arm veins. After a baseline blood draw to measure glucose, insulin, cholesterol, and other factors that may impact or be reflective of the subject's health status (e.g., C-reactive protein), the subject will drink a mixed meal beverage (Ensure original plus ®, 350 calories, 48g carbohydrate, 11g fat, and 16g protein) and blood will be collected in small amounts (less than one half teaspoon) at timepoints 0, 30, 60, 90, and 120 over a two-hour period.

Continuous Glucose Monitoring: The device which was placed on the subject will be removed.

Choline Supplement/Placebo: Subjects will be given enough capsules to last one week and asked to consume 1000 mg (2 x 500 mg tablets) of choline or placebo with a bottle of water every day.

Sessions 5-7, 14-16: (Approximately 30 minutes per session) Garvin Bldg, Suite 1575

Choline Supplement/Placebo: Subjects will be given enough capsules to last one week and asked to consume 1000 mg (2 x 500 mg tablets) of choline or the placebo with a bottle of water every day.

Resting Blood Pressure and Heart Rate: Blood pressure measurements will be made under quiet, comfortable ambient laboratory conditions via mercury sphygmomanometry or an automatic blood pressure monitor. Heart rate will also be determined by an automatic blood pressure cuff. Measurements will conform strictly to American Heart Association guidelines.

Body Mass: Body weight will be measured on a digital scale accurate to +/- 0.01 kg.

Dietary intake analysis (24-hour recall): Subjects will be asked to recall all the food and beverages they consumed in the previous 24-hour period.

After session 10: Following this session, subjects will return to their normal activities for a two-week "washout".

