## 5.0 Study Design and Statistical Analysis Plan

5.1 *Describe the basic study design/approach (e.g., qualitative study using five focus groups of first year students to describe assimilation into the university community; randomized controlled trial of a behavioral change*

*intervention to increase dietary intake of whole grains; pre- post-test evaluation of new pedagogical techniques to improve adult literacy):*

A double-blind randomized 2x3 crossover design with 3 repeated measures in each period will be used. Pre-/post-test evaluation used in each period to evaluate the ingestion of choline/placebo on the effects to cardiometabolic health.

**5.2** *Describe corresponding data analysis plan/approach (e.g., content analysis of focus group transcripts; descriptive analysis followed by linear regression modeling; nonparametric analysis of pre- and post-test measures):*

Data will be examined for the presence of outliers, violations of normality and missing data. Major violations of normality will be corrected with an appropriate transformation procedure. In case of an outlier, rather than transform the data, the outlier will be “Winsorized”, that is, replaced by the most extreme value in the tail of the distribution. Data will be checked for sequence, period and carryover effects. Next, a mixed-effects linear model (using SAS PROC MIXED) will be used to estimate the treatment differences between choline and placebo ( $H_0: \mu_{AB} - \mu_{BA} = 0$ ). Because of the two repeated measurements of the dependent variable in each period, we will treat the multiple observations as nested within individuals. This will allow us to model the various sources of intra-person and inter-person variability, as well as account for the correlation in the nested data to make the correct inference regarding differences between treatments. Confidence intervals (95%) and bootstrapped standard error estimates will be reported for statistical precision and estimation of effect sizes for a larger more comprehensive trial. An identical approach will be used for analysis of other outcomes (e.g., arterial stiffness, etc.).

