## **8.0 Procedures Involved**

*8.1 Describe and explain the study design:*

Using a randomized cross-over design, participants will be given and asked to consume either choline or a placebo (maltodextrin) supplement for four weeks and will consume 1000 mg (500 BID) of choline or placebo per day. Testing will take place over twelve visits. Participants will complete a screening visit and two periods of three-day testing sessions before and after the four-week period of choline and placebo supplement. In between experimental sessions, there will be a two-week “washout”.

*8.2 Provide a description of:*

- *All research procedures being performed*
- *If the study has more than one procedure, session, and/or subject population, describe each procedure, session, and/or study population separately. For complex studies, you are encouraged to include a figure or chart.*

Session 1: Baseline (screening) session (Approximately 2 hours) Garvin Building, Suite 1575

Overnight Fast: Subjects will be asked to avoid eating or drinking anything except water and to avoid consuming any caffeine-containing beverages for 12 hours prior to this visit so that the test results will not be influenced by the food they eat or by the normal digestion process.

Blood Chemistry: A blood draw will be collected for choline concentrations as well glucose, cholesterol, and other factors that may impact or be reflective of vascular function/health. A needle will be inserted in an arm vein to draw blood (approximately 2 tablespoons/draw).

Urine Test: Subjects will be asked to urinate in a small cup. Sodium and other electrolytes, glucose, protein, pH, and whether there are blood cells present will be measured to determine whether it is safe for each individual to participate in the study.

Proof of COVID-19 vaccination: Subjects will be asked to bring their vaccination card against COVID-19 to the laboratory.

Medical History: Subjects will be asked to complete a medical history questionnaire, which will be used to screen for health problems (unstable heart disease) or other reasons (medications which influence study results) that would preclude participation.

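### As written, Section 8.2 dispenses a week of capsules at sessions 4, 10, 13 and 19: five supplies per four-week period, with the session 10 supply falling in the washout

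*Combined protocol and SAP*

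**What the plan says.** Section 8.1 has participants take "either choline or a placebo (maltodextrin) supplement for four weeks", with three test sessions before and three after each supplementation period. Of the gap it says: "In between experimental sessions, there will be a two-week" washout.

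Section 8.2 then describes visits in groups. One group is headed "Session 4, 10, 13, 19: (Approximately 3 hours) Garvin Building, Suite 1575". Its items include the mixed meal test, removal of the glucose monitor ("The device which was placed on the subject will be removed") and a dispensing item: "enough capsules to last one week and asked to consume 1000 mg (2 x 500 mg tablets) of choline or placebo", to be taken every day. The next group, "Sessions 5-7, 14-16: (Approximately 30 minutes per session"), gives a further one-week supply at each visit. The section closes with a line for session 10: "Following this session, subjects will return to their normal activities for a two-week" washout.

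Section 5.1 describes a "Pre-/post-test evaluation used in each period to evaluate the ingestion of choline/placebo". Section 5.2 says the data will be checked for sequence, period and carryover effects.

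**The concern.** Sessions 4 and 13 are the last visits before supplementation starts in each period. Sessions 10 and 19 are the last visits after it. One description serves all four, and the capsule item carries no restriction. The neighbouring items (mixed meal test, monitor removal) do apply at all four visits, so the layout does not mark the capsule item as different.

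Read literally, staff would hand out a week of capsules at session 10, the visit after which the washout begins, and again at session 19, the last visit of the study. The session 10 supply is the one that could affect the trial. If it is a continuation of the period 1 product, subjects randomised to choline first would take choline into the washout, while those randomised to placebo first would take maltodextrin. Any residual choline effect would therefore fall on one sequence only, ahead of the period 2 baseline tests at sessions 11-13. A carryover check may detect such a problem but cannot restore a shortened washout.

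**Working it through.** No formula beyond counting is needed. The inputs are the visit groups in Section 8.2, the four-week and two-week figures in Section 8.1, and the total of 19 visits in Sections 6.1 and 11.1.

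| | Period 1 | Period 2 |
|---|---|---|
| Test visits before supplementation | 2, 3, 4 | 11, 12, 13 |
| Weekly visits | 5, 6, 7 | 14, 15, 16 |
| Test visits after supplementation | 8, 9, 10 | 17, 18, 19 |
| Visits with a dispensing item, as written | 4, 5, 6, 7, 10 | 13, 14, 15, 16, 19 |
| One-week supplies, as written | 5 | 5 |
| One-week supplies without sessions 10 and 19 | 4 | 4 |

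**The plan's own figure.** Four weeks per period is reproduced only when sessions 10 and 19 are left out: sessions 4-7 give four supplies, and so do sessions 13-16. The text as written gives five.

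**Capsules.** Two a day for 7 days is 2 × 7 = 14 per supply.
- As written: 5 × 7 = 35 days and 5 × 14 = 70 capsules per period.
- From the four weeks stated: 4 × 7 = 28 days and 4 × 14 = 56 capsules per period.
- Excess: 70 − 56 = 14 capsules per period, and 14/56 = 25%.
- Whole study: 2 × 70 = 140 capsules against 2 × 56 = 112.

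**Washout.** Two weeks is 14 days, counted from session 10. If the session 10 supply is taken daily from that visit, it covers 7 days and leaves 14 − 7 = 7 supplement-free days.

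**Could the extra supply be a top-up to cover post-testing?** That does not fit. Sessions 8 and 9, where such a supply would be needed, list no dispensing. Session 10 is the last post-test visit of period 1, and session 19 is the last visit of the study.

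**The case against.** The strongest reply is that the protocol, read as a whole, already settles the matter. Section 8.1 places the post-tests after the four weeks of supplement, and Section 8.2 has a specific line putting the washout after session 10. A specific line would normally prevail over a general item in a shared block. The literal reading also defeats itself at session 19, where it supplies a subject who has no further visits. Section 26.1 adds training before enrolment, weekly staff meetings on the protocol and refresher training. Section 7.1 has sealed containers assigned by subject ID. For harm to follow, staff would have to dispense at session 10 despite the washout line, the subject would have to take the capsules, seven days would have to be too short, and the period 2 baseline would have to matter to the analysis. The documents give no elimination or recovery time for choline or TMAO, and Section 5.2 does not say how that baseline enters the model.

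Much of this stands. A drafting slip is the likely cause, misdispensing is not shown, and the size of any bias cannot be stated. The capsule totals rest partly on session 19, which affects no estimate.

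It does not remove the contradiction. The washout line says that subjects go back to normal activities. It does not say that capsules are withheld or returned at session 10. Section 7.1 ties containers to the subject and mentions no visit. Training cannot be assumed to override a written instruction, and the text contains no visit-by-visit dispensing table that would resolve the point.

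**Conclusion.** The concern holds as a contradiction in the written protocol. Section 8.2 lists ten one-week supplies, five per period, against the eight weeks (two periods of four) in Section 8.1. The session 10 supply conflicts with the two-week washout: if dispensed and taken daily from that visit, it halves the supplement-free interval from 14 to 7 days. The session 19 supply counts towards the total but bears on no estimate.

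The effect on the trial is conditional on staff following the text at session 10 and on the pre/post comparison using the period 2 baseline. There is no finding that dosing during the washout was intended or took place. The point should be fixed because it concerns an operative instruction about study product in a crossover trial that depends on its washout.

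**What to change.** Reconcile Section 8.1 with the two dispensing blocks and the washout line in Section 8.2, so that the visits at which capsules are given, the length of supplementation and the washout agree. The amended text should name each dispensing visit explicitly, since a block shared by pre- and post-supplement visits cannot show the difference. The sponsor decides which schedule is intended; no schedule is proposed here.

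The cost is a protocol wording amendment. No visits are added.

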### 8.3 *Describe:*

- *Procedures or safeguards intended to reduce the probability and magnitude of risks. (For example: Reducing the risk of injury in a virtual reality study either by having the subjects sit during the study or by providing an obstacle-free space for walking.)*
- *Be sure to describe all drugs and devices used in the research, when they will be administered or used, and their purpose.*
- *Methods used to collect data about subjects. Please upload all data collection forms to Protocol Management. Some common examples are:*
  - *Screening questionnaires*
  - *Survey(s), including online surveys*
  - *Demographic questionnaire(s)*
  - *Interview guide(s), e.g., questions or pool of questions for semi-structured interviews*
  - *Focus group guide(s)*
  - *Other documents used to collect data*

- Blood Draw: The P.I. or a trained technician will perform all blood draws. Aseptic conditions will be followed during all of the procedures. Universal precautions will be taken in collection and handling of all blood samples. Subjects will be informed that their blood will be analyzed for presence of HIV and Hepatitis, if an experimenter is exposed to their blood.
- Endothelial Function: The risk of low blood pressure during nitroglycerine administration is minimized because the subject is already in the supine position. There is a small risk of a headache, but this will last only a few minutes. Individuals taking Cialis or Viagra cannot participate in this aspect of the study.
- DEXA scan: DEXA procedure will be performed by trained staff. Subjects will be informed of the risk of radiation exposure prior to study enrollment.
- Continuous Glucose Monitor: The placement of the CGM on the subject will be performed by trained staff. This will take place in aseptic conditions, minimizing the risk of any infection.

*8.4 What data will you collect during the study and how you will obtain them? Please include descriptions of electronic data collection, database matching, and app-based data collection:*

- Study data will be collected on data sheets and manually entered into a database (Excel format) on a secure computer.

*8.5 Who will transcribe or code audio and/or video recordings?:*

N/A

*8.6 Include a description of any deception to be used in the study. Include justification for the use of deception (why the deception is necessary), describe the debriefing process, and describe how the study meets all the following criteria for alteration of consent (deception is considered an alteration of informed consent):*

- *The research involves no more than minimal risk to the subjects*
- *The alteration will not adversely affect the rights and welfare of the subjects*

- *The research could not practicably be carried out without the alteration/deception*
- *(Optional but encouraged in most cases) Subjects will be provided with additional pertinent information after participation (i.e., debriefing for studies involving deception)*

N/A

8.7 *If the study involves long-term follow-up (once all research related procedures are complete), describe what data will be collected during the follow up period and when it will occur:*

N/A

## 9.0 Data and Specimen Long Term Storage and Use

9.1 *If you will store data or specimens for future use, describe where you will store the data or specimens, how long they will be stored, and how and by whom the data or specimens will be accessed:*

All data will be stored in a locked cabinet in [name] laboratory the Human Integrative Physiology Laboratory located in Garvin Building, Suite 1575 ([name]) which is also locked with access to authorized personnel only. The computer data will be stored in the locked lab on a computer that is password protected. All de-identified data will be kept indefinitely and there is no need to use specimens for the scope of the study.

9.2 *For specimens, list the data to be stored or associated with each specimen:*

N/A

9.3 *Describe the procedures to release data or specimens outside of the research team, including the process to request a release, approvals required for release, who can obtain data or specimens, and what data will be provided with specimens:*

N/A

9.4 *Describe the identifiers to be included with stored data or specimens, as well as any key or code that could be used to make them identifiable. Describe where the code will be stored, who will have access to it, and when it will be destroyed:*

Codes using a combination of letters and/or numbers will be used to de-identify subjects from their personal information. This de-identified data collection sheet will be stored and locked away and the key will be kept in a locked cabinet separate from the subjects' completed data documents and accessibility will be limited to the PI and Co-PI's.

The people who will have access to this data are the investigators and students involved in the study

De-identified data may be kept indefinitely. Identifiable data and blood samples will be retained before being destroyed for 5 years.

9.5 *Please select the identifiers you will obtain (whether directly from participants or from another source), including but not limited to:*

	Name
	Geographical subdivisions smaller than a state, including street address, city, county, precinct, zip code, and equivalent geocodes (note, the initial three digits of a zip code are not considered identifiable)
	Elements of dates (except year) for dates directly related to an individual, including birth date, admission date, discharge date, date of death, and single year of age over 89 and all elements of dates (including year) indicative of such age (note, such ages and elements may be aggregated into a single category of age 90+)
	Phone numbers
	Fax numbers
	Electronic mail addresses (e-mail)
	Social Security numbers
	Medical record numbers
	Health plan beneficiary numbers

	Account numbers
	Certificate/license numbers
	Vehicle identifiers and serial numbers, including license plate numbers
	Device identifiers and serial numbers
	Web Universal Resource Locators (URLs)
	Internet protocol (IP) address numbers
	Biometric identifiers, including finger and voice prints (audio recording)
	Full face photographic images and any comparable images (including video recording)
	Student record number or identification number
	User name for online or computer accounts
	Any other unique identifying number, characteristic, or code (note this does not mean the unique code assigned by the investigator to code the data): Click here to explain.

